1.1. Objectives, Endpoints, and Estimands

The clinical research objectives, endpoints, and The clinical research objectives, endpoints, and estimands for specific investigations are detailed in the relevant ISA.

1.2. Study Design

The overall design includes 2 components which, used together, constitute the complete protocol for study conduct: the ADMP is a multinational, multicenter, randomized, double-blind, controlled, platform-type master protocol with ISAs to investigate multiple interventions for atopic dermatitis (AD) at the same time or serially over time. ISAs can begin independently of one another as interventions become available for clinical testing. The ISAs can also finish independently of one another, ending, for example, when the ISA has reached its full planned duration or when interim analyses show that an intervention's criteria for futility or success has been met.

Overall, the design includes 2 components which, used together, constitute the complete protocol for study conduct:

- Master Protocol IMMB explains the platform and contains protocol elements common to every investigation in the platform. Common elements include, but are not limited to, the master protocol screening period and master protocol entry criteria; safety monitoring activities and criteria for discontinuation applicable to every ISA; and statistical analysis methods applicable to every ISA.
- The ISAs provide information on the interventions to be studied, for example, intervention-specific screening activities, background information, benefit/risk, and dose justification; intervention-specific study objectives, endpoints, and estimands; and intervention-specific outcome measurements and statistical analysis methods.

2. Statistical Hypotheses

The master protocol provides a framework for evaluating the safety and efficacy of investigational interventions for AD. The ISAs and ISA-SAPs will provide the specific details on the clinical objectives, endpoints, and efficacy estimands of interest.

2.1. Multiplicity Adjustment

Multiplicity adjustment will generally not be performed for ISAs; refer to Section 2.1 of the ISA-SAP for specific details.

3. Analysis Sets

The populations in [Table 3.1](#) are defined for this study. Depending on the ISA, the modified intent to treat (mITT) and/or safety population may distinguish between induction and maintenance periods. For example, a safety population for the induction period and, separately, a safety population for the maintenance period.

Table 3.1. The Minimum Analysis Sets for the ADMP

Participant Analysis Set	Description
mITT	All randomized participants receiving at least 1 dose of study intervention. Participants will be included in the analysis set according to their randomly assigned intervention.
Safety	All randomized participants receiving at least 1 dose of study interventions. Participants will be included in the analysis set according to the intervention they actually received.

Abbreviations: ADMP = atopic dermatitis master protocol; mITT = modified intent to treat.

4. Statistical Analyses

The MP-SAP will specify analyses and methods for

- patient disposition information
- baseline demographic and disease severity information

CCI

- safety analyses applicable across all ISAs.

The ISA-SAP will specify efficacy estimands and corresponding methodology, and other safety analyses.

[figure not shown]
4.1. General Considerations

Statistical analysis of this study will be the responsibility of Eli Lilly and Company or its designee.

Unless otherwise indicated in the ISA-SAP, the following general considerations are used:

- continuous data will be summarized in terms of the number of observations, mean, standard deviation, median, minimum, and maximum
- categorical data will be summarized as frequency counts and percentages
- primary and secondary endpoint analyses will be tested at a 2-sided α level of .05
- baseline values for efficacy analyses will be defined as the last available value before the first dose of study intervention, and
- efficacy and patient-reported outcome analysis models may contain independent variables. These variables may include, but are not limited to, treatment group, baseline disease activity, and geographic region. The ISA-SAP will specify the relevant independent variables.

CCI

CCI

4.2. Participant Dispositions

A detailed description of participant disposition will be provided, including a summary of the number and percentage of participants entered into the study and randomized among screened participants, and number and percentage of participants who complete the study or discontinue among randomized participants. The reasons for discontinuation will be summarized for each ISA. A summary of important protocol deviations will be provided for each ISA.

Depending on the ISA, participant disposition may be described for both the induction and maintenance treatment periods. The ISA and/or ISA-SAP (Section 4.2) will provide details on additional relevant information for participant disposition.

4.3. Primary Endpoint/Estimand Analysis

Please see Section 4.3 of the relevant ISA-SAP.

4.4. Secondary Endpoints/Estimands Analysis

The MP-SAP will focus on two safety analyses: (1) overall safety profile across treatment periods including posttreatment follow-up, and (2) safety profile during induction. The ISA-SAP will define the treatment groups, if relevant, for the overall and induction safety analyses.

Please see Section 4.4 of the relevant ISA-SAP for secondary endpoints and/or estimands for efficacy analyses or ISA-specific safety analyses.

Estimand for overall safety analyses

A secondary clinical question of interest is: what is the difference between active study intervention versus placebo in the number, percent, and/or incidence rates (IRs) of treatment-emergent adverse events (TEAEs) of interest?

The estimand is described by the following attributes:

- Population: participants with moderate-to-severe AD
- Endpoint(s): number, percent, and/or IRs for first TEAEs of interest
- How to account for intercurrent events:
 - Early Permanent Discontinuation of Study Intervention: TEAEs during the posttreatment follow-up will be considered attributable to the study intervention
 - Use of Prohibited or Rescue Medication: TEAEs after the use of prohibited or rescue medication will be considered attributable to the study intervention.

- Assignment to Escape Arm (if applicable): if a participant escapes from placebo to active study intervention, subsequent TEAEs will be attributable to the active study intervention, and
- Assignment to Placebo Withdrawal Arm (if applicable): if a participant is re-randomized from active study intervention to placebo, TEAEs will be considered attributable to the active study intervention until the completion of the study
- Population-level summary: the difference in IRs for TEAEs of interest between participants receiving (rather than assigned to) active study intervention versus placebo, and
- Rationale for estimand:
 - TEAEs of interest for participants receiving active study intervention are considered attributable to study intervention

CCI

- the use of prohibited or rescue medication are potential components of treatment regimens and should therefore be attributable to study intervention.

Secondary estimand for safety during induction period

A secondary clinical question of interest is: what is the difference between the active study intervention versus placebo (or active comparator) in the number, percent, and/or IRs of TEAEs of interest during the induction treatment period?

The estimand is described by the following attributes:

- Population: participants with moderate-to-severe AD
- Endpoint: number, percent, and/or IRs for first TEAE of interest
- How to account for intercurrent events:
 - Early Permanent Discontinuation of Study Intervention: TEAEs during the posttreatment follow-up visits will not be considered attributable to the study intervention, and
 - Use of Prohibited or Rescue Medication: TEAEs after the use of prohibited or rescue medication, regardless of relation to AD, will be considered attributable to the study intervention
- Population-level summary: the difference in IRs for TEAEs of interest between participants receiving (rather than assigned to) active study intervention versus placebo, and
- Rationale for estimand: TEAEs during the induction period provide the most direct and clean comparison of safety across ISAs because the ADMP requires each ISA to have an induction treatment period. The posttreatment follow-up period is not included due to potentially notable differences across ISAs including, for example, maintenance treatment periods.

4.5. Exploratory Endpoints/Estimands Analysis

The MP-SAP will describe the general principals and process for sharing placebo data from historical studies (either completed ISAs in the ADMP or other AD studies with participant-level data). For all other exploratory analyses, please see Section 4.5 of the relevant ISA-SAP.

CCI

4.6. Safety Analyses

For safety analyses, p-values will not be included unless specified in the ISA-SAP.

Table 4.1. Baseline and Postbaseline Period Definitions for Overall and Induction Safety Analyses

Analysis Type	Baseline Period	Postbaseline Period
TEAEs (induction safety analyses)	Starts from informed consent date for IMMB to just prior to the time of first dose.	Starts at the time of first dose of the study intervention and ends at the earliest of the following: 
 • Time of discontinuation from ISA • Time of discontinuation from study drug • Time of completing induction treatment period (time of the first dose in the maintenance treatment period, if relevant, or the date of the last visit in the induction treatment period), or • Database cut-off date for ongoing studies
TEAEs (overall safety analyses)	
Randomized in the initial period: Starts from informed consent date for IMMB to just prior to the time of first dose.
 
Assigned to Escape Arm from Placebo (if applicable): From the informed consent date for IMMB to just prior to the time of first dose of active study intervention on the escape arm.
	
For participants randomized to active study intervention in the initial period or assigned to escape arm from placebo: Starts at the time of first dose of the active study intervention and ends at the earliest of the following: 
 • Time of discontinuation from ISA • Time of ISA completion, or • Database cut-off date for ongoing studies 
 
For participants initially randomized to placebo: Starts at the time of first dose and ends at the earliest of the following: 
 • Time of discontinuation from ISA • Time of ISA completion • Time of first dose on the escape arm (if applicable), or • Database cut-off date for ongoing studies 

Analysis Type	Baseline Period	Postbaseline Period
Laboratory tests and vitals (overall safety analyses)	
Randomized in the initial period: The last available value prior to the first dose of study drug.
 
Assigned to Escape Arm from Placebo (if applicable): The last available value prior to the first dose of active study intervention on the escape arm.
	
For participants randomized to active study intervention in the initial period or assigned to escape arm from placebo: Starts at the time of first dose of the active study intervention and ends at the earliest of the following:
 
 • Time of discontinuation from ISA • Time of ISA completion, or • Database cut-off date for ongoing studies. 
For participants initially randomized to placebo: Starts at the time of first dose and ends at the earliest of the following:
 
 • Time of discontinuation from ISA • Time of ISA completion • Time of first dose on the escape arm (if applicable), or • Database cut-off date for ongoing studies.

Abbreviations: ISA = intervention specific appendix; TEAE = treatment-emergent adverse event.

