4.6.5.2. Vital Signs, Physical Findings, and Other Observations Related to Safety	21
4.6.5.3. Hepatic Safety	22
4.6.5.4. Infections	22
4.6.5.5. Malignancy	24
4.7. Other Analyses.....	24
4.7.1. Subgroup Analyses	24
4.8. Interim Analyses.....	24
CCI [REDACTED]	25
4.9. Changes to Protocol-Planned Analyses	25
5. Sample Size Determination	26
6. Supporting Documentation	27
6.1. Appendix 1: Demographic and Baseline Characteristics	27
6.2. Appendix 2: Definition of Efficacy Endpoints and Patient- Reported Health Outcomes.....	28
6.3. Appendix 3: Laboratory Analytes for Safety Analyses	31
7. References.....	32

Table of Contents

Table		Page
Table 1.1. SAP Version History Summary	4	
Table 3.1. The Minimum Analysis Sets for the ADMP.....	9	
Table 4.1. Baseline and Postbaseline Period Definitions for Overall and Induction Safety Analyses.....	14	
Table 4.2. Tables and Listings Related to Adverse Events.....	17	
Table 4.3. Tables and Figures for Clinical Laboratory Evaluations	20	
Table 4.4. Tables and Figures for Vital Signs and Physical Characteristics.....	21	
Table 4.5. Summary Tables and Figures Related to Hepatic Safety.....	22	
Table 4.6. Summary Tables, Figures, and Listings Related to Infection Safety	24	
Table 6.1. Demographic and Baseline Characteristic Variables.....	27	
Table 6.2. Derivation of Efficacy and Patient-Reported Health Outcomes	28	
Table 6.3. Laboratory Analytes.....	31	

Version History

This Statistical Analysis Plan for Study J4E-MC-IMMB is based on the protocol dated 13MAR2023.

Table 1.1. SAP Version History Summary

SAP Version	Approval Date	Change	Rationale
1	See date on Page 1	Not Applicable	Original version

1. Introduction

The purpose of this Statistical Analysis Plan (SAP) is to describe and specify the analyses relevant across the different intervention specific appendices (ISAs) of the atopic dermatitis master protocol (ADMP). The ADMP-specific SAP (MP-SAP) will specify

1. baseline characteristics of interest
2. safety analyses common across ISAs
 - a. overall safety including the posttreatment follow-up period, which accounts for safety events after dosing stops but drug has not washed out, and
 - b. safety during the induction treatment period, which is common to all ISAs, and
3. analysis framework for borrowing placebo data in the ADMP.

There are no changes to the analyses described in Protocol J4E-MC-IMMB (IMMB).

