4.6.2. Adverse Events

Adverse events (AEs) are recorded in the electronic case report form (eCRF). Each AE will be coded to System Organ Classes (SOC) and Preferred Terms (PT), using the Medical Dictionary for Regulatory Activities (MedDRA) version that is current at the time of the database lock. Severity of AEs is recorded as mild, moderate, or severe.

TEAEs are defined as events that either first occurred or worsened in severity during the postbaseline period defined in [Table 4.1](#). The MedDRA Lowest Level Terms will be used in defining which events are treatment-emergent (TE). The maximum severity for each Lowest Level Term during the baseline period will be used as baseline. TE status in the presence of incomplete data will be determined through the following rules:

- if an AE has missing severity during the baseline period, then the baseline severity will be considered mild for determining TE status
- AEs with missing severity during the postbaseline period will be considered TE regardless of severity during the baseline period, and
- AEs with insufficient data on start date to determine the relevant period (for example, AE start year is the same as the treatment start year, but the AE start month and day are missing) will be considered TE.

For AEs occurring on the first day of the postbaseline period, the day and time of the AE start date will be compared with the dosing day and time. If such a comparison cannot be made due to incomplete day and time information, the AE will be considered TE.

Summaries of TEAE data will at a minimum include

- the number of participants in the safety population of interest
- the number of participants experiencing the event in the safety population of interest, and
- frequency, or percentage, relative to the safety population of interest.

As noted in [Table 4.2](#), some TEAE analyses will also include:

- person-years at-risk during the postbaseline period (years from start of postbaseline period to the first event of interest or the end of the postbaseline period, whichever is first), and
- (exposure-adjusted) IRs and corresponding confidence intervals.

For events that are sex specific, the denominator, computation of percentage, and IR will only include participants of the given sex.

System Organ Class mapping

MedDRA PTs are assigned to a SOC through primary mappings (defined by MedDRA). Thus, MedDRA PTs will appear in only 1 SOC.

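### Does SAP Table 4.1 need changing because it closes the induction adverse-event window at an undefined date of study-drug discontinuation?

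*SAP*

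**What the plan says.** The SAP supplied is the one for the master protocol. It sets two safety analyses.

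- **Induction analysis.** The TEAE window opens at the first dose. It closes at the earliest of leaving the ISA, "Time of discontinuation from study drug", completing induction, or data cut-off. Completion is spelled out in the same cell ("time of the first dose in the maintenance treatment period, if relevant", or else the last induction visit); discontinuation is not. The Section 4.4 estimand for this analysis says, for early permanent discontinuation, that "TEAEs during the posttreatment follow-up visits will not be considered attributable to the study intervention". Its reason is that "The posttreatment follow-up period is not included due to potentially notable differences across ISAs including, for example, maintenance treatment periods".
- **Overall analysis.** The Introduction says it "accounts for safety events after dosing stops but drug has not washed out". Its Section 4.4 bullet says that "TEAEs during the posttreatment follow-up will be considered attributable to the study intervention".

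Section 4.6.2 defines TEAEs as "events that either first occurred or worsened in severity during the postbaseline period", so the window decides what counts. Percentages are taken over the safety population, and person-time for incidence rates (IRs) ends with the window. Three induction summaries give counts and percentages without an IR: the AE overview, maximum severity by Preferred Term (PT), and the summary of infections. The first and third also have overall versions. Maximum severity by PT does not.

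**The concern.** Two things look wrong.

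First, the closing date could be the last dose, the decision to stop, or the ED visit. Table 4.1 also omits the word permanent, and Section 4.4 speaks of follow-up visits. The choice matters most for an event that starts after a dose and leads to no further dosing. If the window closed at the last dose, that event would not be an induction TEAE and would drop out of both the percentage and the IR.

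Second, participants who stop early stay in the denominator while their events after stopping are not counted. Percent-only tables therefore understate the 16-week risk, and more so in the arm with more stopping. Some of the omitted time is exposed time. Protocol Section 5.2 equates 14 weeks with about five half-lives, so one half-life is 14/5 = 2.8 weeks. About 61% of drug remains 2 weeks after a dose (0.5^(2/2.8)) and 37% after 4 weeks (0.5^(4/2.8)).

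The overall analysis cannot replace a 16-week comparison, because placebo time there ends at the first escape dose while active arms run to the end of the ISA.

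**Working it through.** **What the date most plausibly means**

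- When the documents mean a dose date, they say dose. Table 4.1 does so for the window's start, and Protocol Section 4.1 does so when timing follow-up visits from the last dose.
- When they date discontinuation, they use an event. Protocol Section 9.3.1 places entry to the posttreatment period at Week 44 or the ED visit. Attachment 5 counts days from the decision to discontinue early. Section 7.1.2 requires discontinuation before a prohibited AD therapy starts.
- Both follow-up visits come after the ED visit (Protocol Section 4.1). A window ending at the decision or ED visit therefore matches the Section 4.4 exclusion of follow-up. The rationale sentence in that estimand itself says period, not visits.
- Section 4.4 names permanent discontinuation, so a temporary interruption would not close the window.

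On this reading, an event that causes stopping starts before the window closes and is counted.

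**Size of the percent-only shortfall**

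The plan states no figure to reproduce. Inputs:

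- From Protocol Section 4.1: 16 weeks of induction, 96 + 68 + 28 = 192 planned on active drug and 68 on placebo.
- Assumed: true 16-week risk p equal in both arms, a constant hazard, and a proportion d stopping uniformly over 16 weeks.

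With H = −ln(1 − p), a stopper has an event before stopping with average probability 1 − p/H. The percentage seen is

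(1 − d)p + d(1 − p/H).

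For p = 30%, H = 0.3567 and 1 − p/H = 0.1589:

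- d = 20%: 0.8 × 0.30 + 0.2 × 0.1589 = 27.18%
- d = 5%: 0.95 × 0.30 + 0.05 × 0.1589 = 29.29%

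The standard error of the difference is √[p(1 − p)(1/192 + 1/68)] = 6.47 points, so the 2.12-point gap is 0.33 of it. In the same way:

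| True risk | Seen, d = 20% | Seen, d = 5% | Gap (points) | SE (points) | Gap/SE |
|---|---|---|---|---|---|
| 10% | 9.02% | 9.75% | 0.74 | 4.23 | 0.17 |
| 30% | 27.18% | 29.29% | 2.12 | 6.47 | 0.33 |
| 50% | 45.57% | 48.89% | 3.32 | 7.06 | 0.47 |

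Gaps are taken before rounding. The one table with no overall version is by individual PT, so the lower risks are the relevant ones. At p = 5% the same formula gives about 0.4 points, or 0.12 of a standard error. A second model, with exponential stopping and a wider contrast of 10% versus 30%, gives gaps of 1.1, 3.1 and 4.8 points at risks of 10%, 30% and 50%.

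**Effect on the IR**

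With a constant hazard and stopping unrelated to the event, events and person-time are cut together. At p = 30% the true rate is 0.3567/16 = 0.0223 per week, and simulation with 20% stopping returns 0.0223. At 50% risk and 30% stopping, the simulated percentage falls to 42.9% while the rate stays at 0.0433 per week, its true value.

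**Effect of the last-dose reading**

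If the decision came 1, 2 or 4 weeks after the last dose (assumed, since the dosing interval is redacted), p = 30% with d = 20% would read 26.81%, 26.47% or 25.84% instead of 27.18%. That is 0.4, 0.7 or 1.3 points lower, before allowing for events that themselves cause stopping.

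**Where events after stopping are reported**

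- Overall analysis: followed to ISA completion, with IRs by PT within organ class.
- Table 4.2 listings: SAEs and AEs leading to permanent discontinuation, tied to neither window; the latter are taken from the disposition form.
- Table 4.6: a listing of serious infections.
- Section 4.6.3: narratives through the end of participation for deaths, SAEs and permanent discontinuations due to AEs.

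**The case for a change.** The best case for a change is that the rationale in Section 4.4 rests on differences between ISAs after induction, whereas the time lost here lies within Weeks 0 to 16, which every ISA shares. Counting stoppers' events to Week 16 would need no new data. AEs are collected at the ED visit and at two follow-up visits that are required of everyone randomised.

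Part of this stands. Neither document supplied defines the date, and the date drives both TEAE status and person-time. Maximum severity by PT, and the tabulated detail for infections of interest, have no overall version.

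The inference from it does not stand. Someone who stops early leaves treatment and moves to posttreatment follow-up (Protocol Section 6.9.1), possibly to start a prohibited AD therapy (Section 7.1.2), so the period that Section 4.4 sets aside does include that time. Counting to Week 16 answers a different question from the one the SAP chose, and at a price. Visits thin out to the ED visit and then about 8 and 12 weeks after the last dose. Some added events would arise at low drug levels or on other therapy. Anyone whose last dose came before Week 4 would finish follow-up before Week 16. An added table is a matter of preference.

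**Conclusion.** No change to the plan follows. The undefined date is missing detail that an analyst would fill from the decision or ED-visit date, in line with the protocol's own usage. The last-dose reading, the only one that would lose events that cause stopping, fits the wording poorly. The on-treatment window is a deliberate estimand choice with the IR difference as its measure. The percent-only tables beside it are descriptive, and Section 4.6 plans no p-values unless the ISA-SAP asks for them.

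The shortfall is modest: 0.7 to 3.3 points between arms at risks of 10% to 50% with 20% versus 5% stopping, which is less than half a standard error throughout. These figures rest on assumed stopping rates, a constant hazard and equal true risk. The real direction and size are unknown. The IR result also needs stopping to be unrelated to the event. The master protocol and the FR01 ISA-SAP were not available and may already settle the date.
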